## 5.1 Schedule of Procedures by Visit

Please refer to [Table 2](#) and [Table 3](#) for a schematic of the schedule of visits and procedures.

### 5.1.1 Informed Consent and Patient Privacy

The study will be discussed with the patient and patient's impartial witness or legally acceptable representative. A patient wishing to participate must give informed consent and authorization prior to any study-related procedures. The patient must also give authorization (US only) and other written documentation in accordance with the relevant country and local privacy requirements (where applicable) prior to any study-related procedures or change in treatment. Each patient that provides informed consent and assent will be assigned a patient number that will be used on patient documentation throughout the study.

Due to the COVID-19 pandemic, it is possible that protocol modifications may become necessary. If this situation arises, in addition to the study informed consent, additional verbal consent may be obtained prior to these adaptations or substantial changes in study conduct in accordance with local regulations.

### 5.1.2 Screening Visit

Prospective patients will be screened for eligibility up to 45 days prior to enrollment and the procedures will be performed as specified below. If convenient, the Screening and Baseline visits may be combined.

It is the investigator's responsibility to review the results of all laboratory tests as they become available. This review will be documented by the investigator's dated signature on the laboratory report. For each abnormal laboratory test result in which the value of the test lies outside the normal range (see [Appendix 2](#) for reference values), the investigator needs to ascertain if this is an abnormal (ie, clinically significant) result for the individual subject. The investigator may repeat the laboratory test or request additional tests to verify the results of the original laboratory

tests. If the laboratory value is determined by the investigator to be clinically significantly abnormal for that subject, the subject will be excluded from the study.

Records will be maintained of those individuals who are screened but do not meet the eligibility criteria for participation in the study.

- Informed consent and authorization
- Ophthalmic and medical history
- Concomitant medications and procedures
- Physical examination
- Pregnancy test (blood)
- Draw blood sample
- ECG
- Chest X-ray
- Visual acuity
- FFST (full field sensitivity test)
- Object detection and discrimination
- Complete ophthalmic examination
- IOP
- SD-OCT
- ERG
- AE review

### **5.1.3 Baseline Visit**

- Confirm patient still consents
- Ophthalmic and medical history
- Concomitant medications and procedures
- AE review
- Pregnancy test (blood)
- Draw blood sample

- Visual acuity
- FFST
- Object detection and discrimination
- Pupillometry (at selected sites)
- Ambulation
- Complete ophthalmic examination
- IOP
- SD-OCT
- Dilated color fundus photography and autofluorescence
- VEP
- Quality of life questionnaire

#### **5.1.4 Treatment Visit (Day 0)**

- Ophthalmic and medical history (pre-injection)
- Concomitant medications and procedures
- AE review

- [REDACTED]
- [REDACTED]
- [REDACTED]

#### **5.1.5 Post Injection Visit (Day 1)**

[figure not shown]
- Concomitant medications and procedures
- AE review

- [REDACTED]
- [REDACTED]
- [REDACTED]

 IOP measurements will be performed pre- and post-injection in the study eye only. After the intravitreal injection, the patient will remain in the supine position and IOP will be monitored for at least 30 min. In the event that the IOP is 30 mmHg or above, this will be managed according to Section 5.3.2.

**5.1.6 Day 7**

[figure not shown]
- Concomitant medications and procedures
- AE review

[figure not shown]
**5.1.7 Month 1**

- Concomitant medications and procedures
- AE review

**5.1.8 Month 3**

- Concomitant medications and procedures
- AE review

### 5.1.9        Month 6: Primary Endpoint

- Concomitant medications and procedures
- AE review

### 5.1.10       Month 9

- Concomitant medications and procedures
- AE review
- [Redacted]

A black vertical bar on the left side of the page, with a series of small black dots aligned vertically along its top edge.

## 5.1.11 Month 12

[figure not shown]
- Concomitant medications and procedures
- AE review

5.1.12 Month 18

- Concomitant medications and procedures
- AE review

### 5.1.13 Month 24 (or Early Termination) Visit

- Concomitant medications and procedures
- AE review

### 5.1.14 Long-term Follow-up Visits

Patients completing the Month 24 visit will participate in long-term follow-up visits. Patients will be asked to report any AEs that occur during this 3-year follow-up period. At Months 36, 48, and 60, patients will undergo the following study assessments conducted at yearly clinic visits:

- Concomitant medications and procedures
- AE review
- Visual acuity
- Complete ophthalmic examination

The procedures for these assessments will be the same as they were for the core study assessments.

## **5.2 Description of Study Procedures**

### **5.2.1 Informed Consent**

During the Screening visit, prospective patients will be invited to provide written informed consent prior to any screening evaluations. An investigator or study coordinator will provide a full explanation of the study, including potential risks of participation and that they may withdraw from the study at any time and for any reason without jeopardizing their future treatment, and an investigator will provide answers to all questions raised by the prospective patient. For those with low vision, a verbal consent will be read out. After ensuring that all questions have been answered, written documentation of the informed consent decision will be obtained and the consent form will be countersigned by a witness to indicate informed consent was obtained.

No study-related procedures will be performed until after informed consent/assent is obtained.

### **5.2.2 Medical History (Review)**

These will comprise:

- Documentation of presenting complaints, and history thereof
- Ocular medical and surgical history
- General medical and surgical history
- Current medication use (ocular and other)

### **5.2.3 Concomitant Medications and Procedures**

All medications and procedures will be recorded on the electronic case report form (eCRF). If the permissibility of a specific medication/treatment is in question, the investigator is to contact Allergan. Given the ongoing COVID-19 pandemic, selected non-live vaccines (e.g., mRNA, non-replicating viral vector, protein subunit) to prevent Severe Acute Respiratory Syndrome Coronavirus 2 (SARS-CoV-2) infection may be administered during screening or the treatment period, as long as components of the vaccine are not contraindicated.

The decision to receive a locally available vaccine is to be based on local guidance and an individual discussion between the treating physician and the subject.

The potential impact of RST-001 on SARS-CoV-2 vaccination is unknown.

#### **5.2.4 Adverse Event Review**

All AEs will be recorded at each study visit. COVID-19 infections should be reported as AEs.

#### **5.2.5 Physical Examination**

A complete physical examination will be performed at the Screening visit, 6 months, and at 24 months (or early termination visit), to include vital signs (oral temperature, heart rate, respiratory rate and blood pressure), height, weight and examination of major organ systems (head/eyes/ears/nose/throat, neck, cardiovascular, respiratory, abdomen, musculoskeletal/extremities, skin, lymph nodes and neurological).

Symptom-specific examinations may be carried out and recorded during the study as needed.

#### **5.2.6 Pregnancy Test**

Women of childbearing potential will undergo blood serum beta-hCG testing, to be analyzed at the site's preferred certified laboratory.

#### **5.2.7 Blood Sample**

A venous sample will be collected from a peripheral vein and laboratory tests will be conducted at the preferred certified laboratory.

Blood sample testing will include hematology (hemoglobin, hematocrit, white blood cell count with differential and platelet count), chemistry panel (sodium, potassium, chloride, total protein, albumin, calcium, phosphorous, glucose, blood urea nitrogen (BUN), creatinine, total bilirubin, alkaline phosphatase, lactate dehydrogenase (LDH), aspartate aminotransferase (AST) and alanine aminotransferase (ALT)), liver function test panel, and RST-001 immunogenicity testing. Instructions for shipping venous blood for immunological analysis are detailed in the Study Procedures Manual.

#### **5.2.8 ECG (Electrocardiogram)**

A standard 12-lead ECG will be performed. An interpretation of the ECG will be performed by a qualified physician, and a signed report will be issued.

#### **5.2.9 Chest X-ray**

A standard posterior anterior (PA) chest x-ray will be performed. An interpretation of the x-ray will be performed by a qualified physician, and a signed report will be issued.

### **5.2.10 Visual Acuity**

The visual acuity of each eye will be measured using an electronic visual acuity (EVA) Early Treatment for Diabetic Retinopathy Study (ETDRS) testing protocol, or low vision assessment of hand motion and light perception as described in the Study Procedures Manual.

### **5.2.11 Full Field Sensitivity Testing (FFST)**

Full field sensitivity testing will be performed using the Espion ColorDome™ LED full-field stimulator (Diagnosys LLC, Lowell, MA) ([Klein M, Birch DG, 2009](#)) according to the procedures outlined in the Study Procedures Manual.

### **5.2.12 Object Detection and Discrimination**

Patients will perform these two tests concurrently, first identifying if a light displayed on an LED screen can be seen and then if a series of standard images (square, circle, triangle, or star) presented on the screen can be identified. The color of each shape will either be red or blue. For each image tested, the shape, color, and threshold intensity will be recorded.

### **5.2.13 Pupillometry (at Selected Sites)**

The pupil responses of both eyes will be tested using a pupillometry system as described in the Study Procedures Manual.

### **5.2.14 Ambulation**

A patient's ability to navigate within a room will be evaluated according to the procedures outlined in the Study Procedures Manual.

### **5.2.15 Complete Ophthalmic Examination**

A complete ophthalmic examination will be performed in both eyes at the Screening and Baseline visits and at each visit after study treatment administration. The examination will include a slit lamp biomicroscopic evaluation of the conjunctiva, cornea, anterior chamber, iris, and lens. The posterior segment and fundus will also be evaluated through dilated pupils by indirect ophthalmoscopy. Intraocular pressure will be measured using Goldmann applanation tonometry or a hand held tonometer (using the same instrument for each patient throughout the study, when possible). If Goldmann applanation tonometry is used to measure IOP, then it must be performed after fundus photography and autofluorescence to prevent fluorescein dye from interfering with the images.

### **5.2.16        Intraocular Pressure (IOP)**

IOP measurements will be performed in both eyes at every study visit except on treatment day (Day 0), where there will be a pre- and post-injection IOP measurement in the study eye only. After the intravitreal injection, the patient will remain in the supine position and IOP will be monitored for at least 30 minutes. In the event that the intraocular pressure is 30 mmHg or above, it will be managed according to Section 5.3.2.

### **5.2.17        Dilated Color Fundus Photography and Autofluorescence**

A standardized procedure for the collection of single, non-stereo images of the fundus of both eyes will be obtained. Color and autofluorescence images of the fundus will be maintained at the site until completion of Phase 2a.

### **5.2.18        Spectral Domain Optical Coherence Tomography (SD-OCT)**

Retinal anatomy of both eyes will be evaluated by SD-OCT scans at the [REDACTED] [REDACTED]. Additional SD-OCT scans may be obtained at the discretion of the investigator. Each SD-OCT will be obtained using the site's preferred macular scanning protocol. Use of the same instrument throughout the study for a given patient is recommended.

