**3.15.3.2 Exclusion Criteria**

Patients will **not** be excluded if the molecular diagnosis underlying their RP is not known or if there is presence of macular edema due to advanced RP.

However, any one of the following will exclude patients from being enrolled into the study:

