### **6.2.1        Intraocular Inflammation and Immunogenicity Related to RST-001**

During the study, evidence of immune response to RST-001 will be monitored by systemic measurement of humoral and cellular immunity as follows:

These tests will be performed at several timepoints during the study:

There is no diagnostic test available for ocular immunogenicity. Instead, clinical evidence suggestive of immunogenicity will be gathered. Examination findings such as reduced visual acuity in the study eye, intraocular inflammation, uveitis, retinal vasculitis, retinal edema, hemorrhage, exudation and/or detachment will also be gathered. Additional evaluations such as OCT and fluorescein angiography may also aid the clinical identification of an immune response.

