## **11 Data Analysis and Statistical Considerations**

### **11.1 Primary (Safety) Endpoint**

The primary endpoint is safety at 6 months, as assessed by

Visual function measures:

- Change in visual acuity in the study eye
- Change in full field sensitivity in the study eye

- Change in ambulation
- IOP measurements in the study eye
- Changes in anatomical parameters as measured in the study eye by:
  - Fundus photography
  - Spectral domain-OCT (SD-OCT)

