### **11.2.2.2 Spectral Domain-OCT (SD-OCT)**

Qualitative assessment of the change in retinal cross-sectional appearance from Baseline to [REDACTED]

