11.2 PRIMARY OCULAR SAFETY MEASUREMENTS

The following visual function measures at 6 months are considered primary safety endpoints. They will be listed and summarized by treatment group separately in each phase.

- Change from baseline in visual acuity in the study eye
- Change from baseline in full field sensitivity in the study
- Change from baseline in ambulation
- IOP measurements in the study eye
- Changes from baseline in anatomical parameters as measured in the study eye by:
 - Fundus photography - Qualitative assessment of the retinal appearance
 - Spectral domain-OCT (SD-OCT) - Qualitative assessment of the retinal cross-sectional appearance

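### SD-OCT is a 6-month primary safety measure with only an ungraded qualitative reading of site-chosen scans, and the SAP's grade-increase table cannot show new or worsening macular fluid

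*Protocol*

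**What the plan says.** Protocol 11.1 lists, under the 6-month primary safety endpoint, "Changes in anatomical parameters as measured in the study eye by" fundus photography and SD-OCT. It names no parameter. SAP 11.2 gives the same items primary status ("The following visual function measures at 6 months are considered primary safety endpoints"), promises that they will be listed and summarized by treatment group, and defines the OCT item as "Spectral domain-OCT (SD-OCT) - Qualitative assessment of the retinal cross-sectional appearance". The secondary endpoint in Protocol 11.2.2.2 is worded alike: "Qualitative assessment of the change in retinal cross-sectional appearance from Baseline to" later visits. SAP 11.3 follows it.

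On acquisition, Protocol 5.2.18 has both eyes scanned, using each site's "preferred macular scanning protocol. Use of the same instrument throughout the study for a given patient is recommended".

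On the condition of interest, Protocol 3.15.3.2 says that patients are not excluded "if there is presence of macular edema due to advanced RP". Protocol 6.2.1 notes that no diagnostic test exists for ocular immunogenicity, so clinical signs are collected instead: "retinal vasculitis, retinal edema, hemorrhage, exudation and/or detachment will also be gathered". OCT is mentioned there as something that may help.

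SAP Table 11.4-2 records intraretinal and subretinal fluid at the macula as ophthalmoscopy findings, with severity marked as not applicable. The one tabulation that SAP 11.4 plans for examination findings counts patients whose grade rises by more than one step from baseline.

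**The concern.** A measure with primary status should have a stated variable, a stated way of calling a change, and images that can be compared between visits. SD-OCT here has none of the three. The reading is an impression without a scale, made by people who know the dose and the treated eye (Protocol 4.5). The scan pattern is left to the site, and nothing requires it to stay the same from visit to visit.

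The gap falls on a risk that the protocol itself raises. The dog study in Protocol 3.6.2.1 found intraocular inflammation that increased with dose, including retinal inflammation on microscopy at the high dose. If retinal or macular edema develops after injection, or if edema present at entry gets worse, the summary tables may not show it. Conversely, a change of device or scan pattern may look like a change in the eye.

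**Working it through.** The plan gives no figure to reproduce: there is no standard deviation, threshold or power for SD-OCT. The check is to compare the sections and follow a macular fluid finding through the planned outputs.

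**1. Is a thickness variable specified?** No. Protocol 11.1 says only anatomical parameters. SAP 11.2 makes the Month 6 reading qualitative, and Protocol 11.2.2.2 and SAP 11.3 do the same for the other visits. Neither document names a thickness or volume, a grading scale, a threshold for change or a central reader. The redactions in these OCT sections stand where visit times would be expected, so they are unlikely to hide a variable.

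**2. Are the scans standardized elsewhere?** Not in these documents. The sections on visual acuity, full-field sensitivity, pupillometry, ambulation and VEP (Protocol 5.2.10, 5.2.11, 5.2.13, 5.2.14, 5.2.20) refer to the Study Procedures Manual, and the ERG section (5.2.19) refers to the ISCEV standard. Section 5.2.18 refers to neither.

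**3. Where would macular fluid appear?**

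| Planned output | New fluid | Worsening of fluid present at baseline |
|---|---|---|
| Grade-increase table (SAP 11.4) | Not shown: no grade exists, so none can rise | Not shown, for the same reason |
| Listing of ophthalmoscopy findings | Shown as present | Present at both visits; amount not shown |
| Qualitative SD-OCT reading | Shown if the reader remarks on it | Shown if the reader remarks on it; no scale |
| Adverse events | Shown if reported | Shown if reported, subject to step 4 |

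**4. The adverse event route.** Protocol 8.1.1 tells investigators not to report worsening that they judge unequivocally due to the disease, where the sign is collected as an efficacy variable, unless it exceeds the expected natural course. The edema allowed at entry is by definition due to RP, and SD-OCT is among the secondary endpoints. Section 9 does not list SD-OCT as an efficacy assessment, so whether the exemption applies is open to argument. It still leaves a way for worsening edema to go unreported.

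**5. Cost of a numeric variable.** Two numbers (central thickness and volume) for each of two eyes make 2 x 2 = 4 CRF entries per patient per scanning visit, from scans already taken.

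**The case against.** The strongest objection concerns stakes. The only criterion by which the therapy is called safe is the absence of a related grade 3 or greater adverse event (Protocol synopsis, SAP 5.0). SAP 5.0 places SD-OCT among other safety measurements, Phase 1 has about 3 patients per dose group, and no decision rule uses the OCT reading. This stands, and it limits the point to the quality of descriptive safety reporting.

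Second, macular fluid is a prespecified ophthalmoscopy finding, and investigators may add OCT or angiography at their discretion (Protocol 5.2.18, 6.1.1.2). That is a fair answer for the care of an individual patient. It is not an answer for the summaries, because a finding without a grade cannot enter a table of grade increases.

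Third, a site-chosen scan may be adequate for a qualitative reading, and a numeric thickness is more exposed to a change of device. This is correct. It is the reason for restricting comparisons to the same device within a patient.

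Fourth, automated segmentation can fail in advanced RP, and someone who knows the treatment must flag the failures. This also stands. A thickness value depends less on the reader, but is not free of the reader.

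Fifth, the table and listing specifications are in a separate document (SAP 4.0) that is not available here. The point is therefore confined to what the protocol and SAP specify.

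**Conclusion.** The point holds as a worthwhile, inexpensive improvement. It does not undermine the trial's safety criterion. A measure with primary status has no graded or numeric definition and no requirement for consistent imaging, and the one planned tabulation of examination findings cannot show macular fluid, whether new or worsening.

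A reader might infer more than the documents support:

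- **That thickness is never measured, or that the reading is yes/no.** Sites may hold thickness values, and nothing makes the reading binary. What can be said is that no thickness analysis is specified.
- **That the missed change can be sized in micrometres.** The documents give no repeatability figure. The Screening and Baseline scans do not cleanly supply one: their windows (Days -45 to -8 and -7 to -1) allow a gap of up to 45 - 1 = 44 days, in which edema may truly change. The two visits may also be combined, and devices may differ between sites.
- **That central thickness would reveal thinning of the ganglion cell layer, the treatment target.** It is a whole-retina value and does not isolate that layer.
- **That listing thickness beside acuity would separate clearing of edema from a drug effect.** With no control group it cannot attribute a gain. The better-vision Phase 2a eyes are enrolled only if the DSMC sees no benefit in Phase 1.

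The conclusion assumes that the site devices report a central macular thickness, and that the macular edema allowed at entry overlaps with the retinal edema listed as an immune sign. The two terms are not identical.

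**What to change.** 1. **Protocol 5.2.18:** require the instrument and scan pattern used at the patient's Baseline at all later visits, and document exceptions. For scans already taken, record what was used.
2. **SAP 11.2 and 11.3:** keep the qualitative reading. Add, descriptively, within-patient change from baseline in device-reported central macular thickness, and in macular volume where the scan gives it, for study and fellow eye, same device only. Report unreliable segmentations as not measurable and show the number measurable.
3. **SAP 11.4:** tabulate ungraded macular fluid findings as new, or as already present at baseline, so that they are not lost from the grade-increase table.
4. **Listing:** for eyes with edema at baseline, show thickness change beside acuity change, labelled as an aid to interpretation.

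As a minor addition, name autofluorescence in the fundus photography listing. It is an ocular safety measurement in Protocol 6.1.1, but neither the Protocol Section 11 endpoints nor the SAP Section 11 analyses mention it.

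The cost is protocol and SAP wording and two more CRF numbers per eye per scan, with no added procedure or reader. The downside is that some scans in advanced RP will not be measurable. The SAP is written to Amendment 2 and must be updated to the current protocol in any case. Protocol 11.3.6 allows the analysis plan to be finalized up to the single database lock.
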